10. STATISTICS

10.1. SAMPLE SIZE CALCULATION

Simon-II optimal two-stage design was applied for sample size estimation. We hypothesise that the experimental therapy will improve the probability of expected objective response rate in refractory settings, from less than 5 % in previous reports, to 20 % in the current study. With 80 % of power (0.2) and unilateral alpha (0.1), 24 patients per cohort are needed to demonstrate the primary hypothesis. The Simon-II design suggested the observation of ≥ 1 patient with objective response within the first nine patients included in the first stage. If ≥ 1 out of nine patients in each cohort achieve an objective radiological response in the first stage, the study will continue to recruit 15 additional patients up to 24 patients per cohort. If ≥ 3 out of a total of 24 patients achieve a radiological objective response at the final analysis, the study should be declared positive. If stage I is reached only in one cohort, recruitment will continue in the successful cohort and stopped in the non-effective cohorts.

10.2. STUDY ENDPOINTS

10.2.1. Primary endpoint

Overall Response Rate (ORR): includes patients with partial (PR) and complete response (CR) as best response according to RECIST v 1.1.

10.2.2. Secondary endpoints

- **Safety profile of cabozantinib and atezolizumab:** The number of patients with AEs and SAEs, changes in laboratory values, vital signs, ECGs, and results of physician examinations graded according to the CTCAE v 5.0. This will be analysed using descriptive statistics techniques such as frequency and contingency tables. The final statistical analysis of this endpoint is expected to be performed within 6 months after database closure, which is expected at 12 months after last patient inclusion. However, interim analysis may be performed when analysing other primary endpoints.
- **Duration of response (DOR) as per RECIST 1.1:** DOR calculated as the time from the date of first documented CR or PR to the first documented progression or death due to underlying cancer.
- **Progression-free Survival (PFS):** Median Progression free survival (mPFS) is defined as the time from the date of inclusion to the date of the first documented disease progression or death due to any cause, whichever occurs first. PFS will be determined based on tumour assessment (RECIST version 1.1 criteria). The local Investigator's assessments will be used for analyses. Patients who are alive and have not progressed at the last follow-up will be censored at the date of the last available image determination (CT Scan or MRI). Patient with no additional image test other than that at baseline will be censored to the day after inclusion.
- **Overall Survival (OS):** Median Overall Survival (mOS) is calculated as the time from date of inclusion to date of death due to any cause.
- **Biomarkers:** To be determined according to study results and Sponsor feasibility.
- **Quality of Life (QoL):** Quality of Life will be analyzed descriptively by QoL questionnaires (EQ-5D-5L, EORTC QLQ-C30, see appendix 2 and 3).

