8.2.4.2. Overall Survival (Long term follow-up)

Follow-up after disease progression will be carried out according to local practice. The follow-up period according to this protocol is 12 months considering last patient inclusion. Information on subsequent treatments should include the list of post-treatment therapies, the drugs administered, the date of initiation/discontinuation of each drug and date of progression. All the data will be recorded in the medical record and in the eCRF.

Survival information may be obtained through telephone contact with the patient, patient's family or by contact with the patient's current physician. Survival data will be collected up to the time of the final overall survival (OS) analysis, and at this point, Investigators will be notified that no further data collection for the study is required.

The status of ongoing, withdrawn (from the study), and lost to follow-up patients at the time of an OS analysis should be obtained by the site personnel by checking the patient's notes and hospital records, contacting the patient's general clinician, and checking publicly available death registries.

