2.5.2. SECONDARY EFFICACY ANALYSIS

Duration of response (DOR) as per RECIST 1.1: DOR calculated as the time from the date of first documented CR or PR to the first documented progression or death due to underlying cancer.

Progression-free Survival (PFS): Median Progression free survival (mPFS) is defined as the time from the date of inclusion to the date of the first documented disease progression or death due to any cause, whichever occurs first. PFS will be determined based on tumour assessment (RECIST version 1.1 criteria).

Overall Survival (OS): Median Overall Survival (mOS) is calculated as the time from date of inclusion to date of death due to any cause.

Biomarkers: To be determined according to study results and Sponsor feasibility.

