2.5.2.2 PROGRESSION FREE SURVIVAL

The 6 months progression-free survival rate will be estimated and plotted using the Kaplan-Meier product-limit method, along with their corresponding log-log transformed 95% confidence intervals.

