2.5.2.2.1 Progression free survival ITT POPULATION

In the ITT population (n=XX), at 6 months the proportion of patients that survived without PD or death was XXXX with a CI95% XXXX-XXXX. The overall median of PFS was XXX months (CI95% XXX-XXX).

Table 180. Progression free survival at 6 and 12 months (ITT)

	N events	Patients at risk	% estimated cumulative survival ratio ¹	95% CI	% of PFS
at 6 months	Cohort 1				
	Cohort 2				
	Cohort 3				
	Cohort 4				
	Cohort 5				
	Cohort 6				
at 12 months	Cohort 1				
	Cohort 2				
	Cohort 3				
	Cohort 4				
	Cohort 5				
	Cohort 6				
Estimated PFS ¹	N	N (%) events	Median (months)	Standard error	95% CI
	Cohort 1				
	Cohort 2				
	Cohort 3				
	Cohort 4				
	Cohort 5				
	Cohort 6				

1: Estimated using Kaplan-Meier product-limit method

[figure not shown]
Table 181. Progression free survival events at 6 months (ITT)

	PFS event	N (%, CI95%)
Cohort 1	Without PD/Death	
	PD	
	Death (without previous PD)	
Cohort 2	Total	
	Without PD/Death	
	PD	
Cohort 3	Death (without previous PD)	
	Total	
	Without PD/Death	
	PD	
	Death (without previous PD)	
	Total	

Sponsor: Grupo Español de Tumores Neuroendocrinos y Endocrinos (GETNE)

	PFS event	N (% , CI95%)
Cohort 4	Without PD/Death	
	PD	
	Death (without previous PD)	
Cohort 5	Total	
	Without PD/Death	
	PD	
Cohort 6	Death (without previous PD)	
	Total	
	Without PD/Death	
	PD	
	Death (without previous PD)	
	Total	

Figure 1 Kaplan Meier curve: PFS (ITT)

Sponsor: Grupo Español de Tumores Neuroendocrinos y Endocrinos (GETNE)

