2.5.2.3.1 OVERALL survival ITT POPULATION

In the ITT population (n=XX), at 6 months the proportion of patients that survived was XXXX with a CI95% XXXX-XXXX. The overall median of OS was XXX months (CI95% XXX-XXX).

Table 184. Overall survival at 6 and 12 months (ITT)

	N events	Patients at risk	% estimated cumulative survival ratio ¹	95% CI	% of OS
at 6 months	Cohort 1				
	Cohort 2				
	Cohort 3				
	Cohort 4				
	Cohort 5				
	Cohort 6				
at 12 months	Total				
	Cohort 1				
	Cohort 2				
	Cohort 3				
	Cohort 4				
	Cohort 5				
Estimated OS ¹	Cohort 6				
	Total				
	N	N (%) death	Median (months)	Standard error	95% CI
Estimated OS ¹	Cohort 1				
	Cohort 2				
	Cohort 3				
	Cohort 4				
	Cohort 5				
	Cohort 6				
Estimated OS ¹	Total				

1: Estimated using Kaplan-Meier product-limit method

[figure not shown]
Table 185. Overall survival events at 6 months (ITT)

	OS event	N (%, CI95%)
Cohort 1	No death at end of follow-up	
	Death	
	Total	
Cohort 2	No death at end of follow-up	
	Death	
	Total	
Cohort 3	No death at end of follow-up	
	Death	
	Total	

Sponsor: Grupo Español de Tumores Neuroendocrinos y Endocrinos (GETNE)

	No death at end of follow-up
Cohort 4	Death
	Total
	No death at end of follow-up
Cohort 5	Death
	Total
	No death at end of follow-up
Cohort 6	Death
	Total
	No death at end of follow-up
Total	Death
	Total
	No death at end of follow-up

Figure 3 Kaplan Meier curve: OS (ITT)

Sponsor: Grupo Español de Tumores Neuroendocrinos y Endocrinos (GETNE)

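### The PFS censoring rule for patients with no post-baseline scan is not limited to living patients, so read literally it turns unscanned deaths into day-1 censorings

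*Combined protocol and SAP*

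**What the plan says.** Protocol section 10.2.2 (Secondary endpoints) defines the PFS event and then gives two censoring sentences.

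- **Event:** documented progression or death from any cause, whichever is first. SAP section 2.5.2 repeats this: "the first documented disease progression or death due to any cause, whichever occurs first".
- **First censoring sentence:** "Patients who are alive and have not progressed at the last follow-up will be censored" at the date of the last available image. It covers only living, progression-free patients.
- **Second censoring sentence:** "Patient with no additional image test other than that at baseline will be censored to the day after inclusion". It mentions neither vital status nor progression.

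The second sentence appears in the same words in the protocol synopsis and in SAP section 1.2.2. SAP section 2.5.2 gives the definition with no censoring rule.

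For the analysis, SAP section 2.5.2.2 states: "The 6 months progression-free survival rate will be estimated and plotted using the Kaplan-Meier product-limit method". Table 180 reports the Kaplan-Meier result per cohort ("estimated cumulative survival ratio") together with a number of events. Table 181 (ITT) and Table 183 (PP) count PFS events at 6 months and include a row that begins "Death (without previous PD".

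**The concern.** A patient who dies before any post-baseline scan satisfies both the event definition and the second censoring sentence. Neither document says which prevails. A programmer who codes the second sentence as written would censor that death on the day after inclusion.

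Three consequences would follow.

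- Early deaths would leave the risk set on day 1, and the per-cohort 6-month PFS rate would be too high.
- Table 180 (Kaplan-Meier) and Table 181 (counts) could treat the same deaths differently.
- PFS could not fall below 100% before the first post-baseline scan in a cohort, while OS, reported in the next section ("at 6 months the proportion of patients that survived was XXXX"), would already be falling.

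The first scheduled scan is at week 12 ± 2, or week 8 ± 2 as an option (protocol section 10.3). Cohort 2 is anaplastic thyroid cancer, for which protocol section 2.1 cites a median survival of 5 months. Cohorts have 9 to 24 patients, so a few such deaths would be visible in the estimate.

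**Working it through.** The plan states no PFS figure to reproduce. Everything below applies only if the second sentence is read literally.

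**1. Size from counts alone (no survival model).** Let k of n patients die unscanned before the first scheduled scan, with no other censoring before then. Let E be the number event-free at a later time, before any further censoring.

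- Deaths as events: PFS = E/n.
- Literal rule: PFS = E/(n−k).
- Ratio: n/(n−k). After the first scan the risk sets are the same, so the factor persists.

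| n | k | n/(n−k) |
|---|---|---|
| 24 | 1 | 24/23 = 1.04 |
| 24 | 3 | 24/21 = 1.14 |
| 24 | 5 | 24/19 = 1.26 |
| 9 | 1 | 9/8 = 1.13 |
| 9 | 2 | 9/7 = 1.29 |

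**2. Worked cohort, n = 24.** Five unscanned deaths between 1.0 and 2.5 months, 6 progressions at week 12, 5 at week 24, and 8 patients event-free to month 12.

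- Deaths as events: 5 + 6 + 5 = 16 events; 6-month PFS = 8/24 = 33.3%.
- Literal: 6 + 5 = 11 events; 6-month PFS = (13/19) × (8/13) = 8/19 = 42.1%.
- Just before week 12, OS = 19/24 = 79% while literal PFS = 100%.

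If Table 181 counts the deaths and Table 180 does not, the two tables show 16 and 11 events for one cohort.

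**3. The direction is not always upward.** Survival is still collected after scanning stops (protocol section 8.2.4.2: "Survival information may be obtained through telephone contact with the patient"), so a never-scanned patient can have a late recorded death. Take n = 9: of 8 scanned patients, 4 progress by month 6 and 4 do not; the ninth is never scanned and dies at month 9.

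- Death as event: at month 6, (4 + 1)/9 = 55.6%.
- Literal: 4/8 = 50.0%.

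**4. Illustration for anaplastic thyroid cancer.** Only the 5-month median survival comes from the documents, and it is a historical figure. Assumed: medians of 8 and 12 months as alternatives (eligibility requires ECOG 0–1), exponential and independent death and progression, a 5-month median time to progression, progression dated at the next scheduled scan, no unscheduled scans, and 1 week = 0.23 months.

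- Dead before the first scan at time t: 1 − 0.5^(t/median). For median 5 and week 12: 1 − 0.5^(2.76/5) = 0.318.
- Correct 6-month PFS is the chance of being alive at 6 months with no progression by the week-24 scan (5.52 months). For median 5: 0.5^(6/5) × 0.5^(5.52/5) = 0.435 × 0.465 = 0.202.
- Literal 6-month PFS divides this by the proportion alive at the first scan: 0.202/0.682 = 0.30.

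| Median OS (months) | Dead before week 12 | Dead before week 8 | Correct 6-month PFS | Literal, 12-week scans | Literal, 8-week scans |
|---|---|---|---|---|---|
| 5 | 32% | 22% | 20% | 30% | 26% |
| 8 | 21% | 15% | 28% | 35% | 32% |
| 12 | 15% | 10% | 33% | 39% | 37% |

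A simulation of 400,000 patients per scenario gave the same rounded PFS values.

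**The case against.** The strongest reply is that the harm needs a strained reading. A censoring date is needed only for patients without an event. The paragraph has already made death an event, and the second sentence can be read as supplying a date for those living, progression-free patients who have no image to be censored at. The row for death without previous progression in Tables 181 and 183 points the same way, as does SAP section 2.5.2, which gives the definition without the disputed sentence.

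This is probably what was meant, but it does not settle the matter. The row is also filled by patients who die after a progression-free scan, so it does not show how unscanned deaths are handled. SAP section 1.2.2 copies the unconditioned sentence, and nothing gives the event definition precedence.

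Other points stand as limits:

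- PFS is secondary and descriptive, with no hypothesis or decision rule attached.
- The anaplastic thyroid percentages rest mostly on assumptions. Only the n/(n−k) factor is nearly assumption-free, and no document gives k.
- The synopsis foresees unscheduled scans. These would reduce the number of patients who die unscanned.

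**Conclusion.** The concern holds: the sentence is wrong as written and should be corrected before analysis. If coded literally, it contradicts the plan's own PFS event definition and inflates later PFS by n/(n−k) for k unscanned deaths before the first scheduled scan, provided nobody else is censored earlier. For 24 patients the factor is 1.04 to 1.26 for 1 to 5 such deaths; for 9 patients it is 1.13 to 1.29 for 1 to 2.

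Under the stated assumptions, 6-month PFS in anaplastic thyroid cancer would read about 6 to 10 percentage points too high with 12-week scans and about 4 to 6 with 8-week scans. The effect is small in slow-growing disease, and late deaths in never-scanned patients can reverse it. The ORR analysis and its decision rule are unaffected. If the analysts already intend to count these deaths as events, no result changes.

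**What to change.** Replace the second censoring sentence in the protocol synopsis, protocol section 10.2.2 and SAP section 1.2.2, and add the same text to SAP section 2.5.2:

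> Death from any cause without prior documented progression is a PFS event on the date of death, whether or not a post-baseline scan exists. Patients who are alive, have not progressed and have no post-baseline scan are censored on the day after inclusion.

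Keeping the not-progressed condition means that a living, unscanned patient with progression by symptomatic deterioration (allowed in rare cases by the protocol section on lack of efficacy or worsening of study disease) is not censored on day 1 by this wording. It does not decide whether such progression counts as a PFS event, because PFS is based on RECIST assessment; the SAP could say so in one further line.

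The cost is two sentences in four places. No table, data collection, sample size or ORR rule changes. Two of the places are protocol text, and protocol section 12.2 sends amendments to the ethics committee. If no amendment is planned, the SAP wording alone, stated to govern the analysis, would settle the result.

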10.3. EFFICACY ASSESSMENT

Body CT scan or MRI will be performed at baseline and every 12 weeks (± 2 week) until progression. Body CT scan or MRI may be performed every 8 weeks (± 2 week) if required by local standard clinical practice

or by investigator criteria, as long as the frequency of assessments is maintained. All target and non-target lesions in the initial evaluation will be measured according to the aforementioned timeline, until disease progression. Imaging tests will be performed using the same method each time.

10.3.1. Time-point efficacy assessment

Table 4. Criteria for disease evaluation for target lesions

CR	Disappearance of all target lesions. Any pathological lymph nodes (whether target or non-target) must have reduction in short axis to <10 mm
PR	At least a 30% decrease in the sum of diameters of target lesions, taking as reference the baseline sum diameters.
PD	At least a 20% increase in the sum of diameters of target lesions, taking as reference the smallest sum on study (this includes the baseline sum if that is the smallest on study). In addition to the relative increase of 20%, the sum must also demonstrate an absolute increase of at least 5 mm. (Note: the appearance of one or more new lesions is also considered progression).
SD	Neither sufficient shrinkage to qualify for PR nor sufficient increase to qualify for PD, taking as reference the smallest sum diameters while on study.

CR = complete response, PR = partial response, SD = stable disease, PD = progressive disease, and NE = not evaluable.

Table 5. Criteria for disease evaluation for non-target lesions

CR	Disappearance of all non-target lesions and normalisation of tumour marker level. All lymph nodes must be non-pathological in size (<10 mm short axis).
Non-CR/non-PD	Persistence of one or more non-target lesion(s) and/or maintenance of tumour marker level above the normal limits.
PD	Unequivocal progression (see comments below) of existing non-target lesions. (Note: the appearance of one or more new lesions is also considered progression).

CR = complete response, PR = partial response, SD = stable disease, PD = progressive disease, and NE = not evaluable.

Table 6. Overall Response Assessment (RECIST 1.1)

Target Lesions	Non-target Lesions	New Lesions	Overall Response
CR	CR	No	CR
CR	Non-CR/non-PD	No	PR
CR	Not evaluated	No	PR
PR	Non-PD or not all evaluated	No	PR
SD	Non-PD or not all evaluated	No	SD
Not all evaluated	Non-PD	No	NE
PD	Any	Yes or No	PD
Any	PD	Yes or No	PD
Any	Any	Yes	PD

CR = complete response, PR = partial response, SD = stable disease, PD = progressive disease, and NE = not evaluable.

10.4. DEFINITION OF STUDY POPULATIONS

Data will be analysed in the following populations:

1. Intent-To-Treat (ITT): All patients that has been enrolled in the trial.
2. Evaluable population per protocol (PP): All patients fulfilling all eligibility criteria without

any protocol deviation that makes patient invalid for the primary endpoint evaluation.

3. Safety population: All patients receiving at least one dose of treatment.

10.5. SAFETY ANALYSIS

The safety population (SP) consists of all enrolled subjects who received at least one dose of study treatment. Patients will be monitored for safety during all the stages of the study. All safety and tolerability assessments will be done at pre-dosing time, unless otherwise specified.

Assessment of adverse events, safety, and toxicity will be performed according to the National Cancer Institute Common Toxicity Criteria (version 5.0) from the time of Informed Consent for the pre-registration phase until the end of study. Safety and tolerability of study medication will be determined by evaluating the type, incidence, frequency, severity, seriousness and causality of adverse effects. Physical examinations, and laboratory tests will also be assessed. Any signs and/or symptoms associated with the worsening of the existing tumour at baseline (in severity or frequency) during the trial should be reported as adverse event.

10.6. STATISTICAL ANALYSIS

For each categorical variable, the results will be summarised by frequencies and percentages. For each continuous variable, the results will be summarised by descriptive statistics such as median, range, and interquartile range or by means, standard deviations, and 95 % confidence intervals (CIs). For proportions, point estimates and exact 95 % confidence intervals will be calculated. For time to event endpoints, Kaplan-Meier estimates at selected time points and corresponding curves will be presented. Time to event is derived relative to the first study treatment administration. Laboratory values will be expressed as absolute values and in grades (ordinal categorical variables) according to NCI CTCAE v 5.0.

Treatment-emergent AE (AEs starting after the administration of study treatment and up to study completion) will be summarised by system organ class and preferred term. Grading will be presented by type and in tables showing the frequency and percentage of the within-patient worst grades. In addition, grade ≥ 3 AEs will be summarised separately. Full analysis details will be outlined in the statistical analysis plan (SAP).

10.7. STATISTICAL METHODS

Analysis will be based on observed data, and missing data for drop-outs are not replaced by methods like LOCF (last option carried forward).

Continuous data will be presented with the number of observations, mean value, standard deviation, minimum, maximum, and median. Categorical data will be presented as counts and percentages. Individual subject data will be listed.

Vital signs, ECG parameters, clinical laboratory data (haematology, serum biochemistry, and urinalysis) will be presented in tabular form. Values outside the reference range will be flagged, and the clinically significantly abnormal values will be listed in tabular form. Adverse events will be tabulated by system organ class and preferred term after medical coding using the according to NCI CTCAE v 5.0.

11. DIRECT ACCESS TO SOURCE DATA/DOCUMENTS

11.1. SOURCE DATA DEFINITION

Source data is defined as all data in original records and certified copies of original records of clinical findings, observations, or other activities in a clinical trial that are necessary for the reconstruction and evaluation of the trial.

The Investigator must keep a file (medical file and original medical records) on paper or electronically for every subject in the trial. It must be possible to identify each subject by using this subject file. This file will contain the demographic and medical information listed below and should be as complete as possible.

- Subject's full name, date of birth, sex, height, and weight
- Medical history and concomitant diseases
- Prior and concomitant therapies (including changes during the trial)
- Trial identification, that is, the Sponsor trial number for this clinical trial, and subject number
- Dates for entry into the trial (informed consent) and visits to the site
- Any medical examinations and clinical findings predefined in this clinical trial protocol
- All AEs
- Date that the subject left the trial including any reason for early withdrawal from the trial or IMP (if applicable).

All documents containing source data must be filed, including, but not limited to CT or MRI scan images, ECG recordings, and laboratory results. Such documents must bear the subject number and the date of the procedure. Where possible, this information should be printed by the instrument used to perform the assessment or measurement. Medical evaluation of such records will be performed as necessary; all evaluations will be documented, signed, and dated by the Investigator.

Electronic subject files will be printed whenever the Monitor performs source data verification. Printouts will be signed and dated by the Investigator, countersigned by the Monitor, and will be secured in a safe place at the site.

According to the directives of the European Parliament 95/46 and Regulation Regulation No. 536/2014 of the European Parliament and of the Council on clinical trials on medicinal products for human use, the information obtained in the course of the clinical trial may only be used by the Sponsor of clinical trial to evaluate the results in compliance with the directive mentioned.

